Finally, micronutrient deficiencies and excess may cause genomic damage, which could be in the same range of magnitude, or even higher, than genomic damage caused by exposure to high doses of environmental genotoxic agents such as carcinogenic agents, ultraviolet radiation and ionizing radiation (Fenech, 2010). Furthermore, since iron is not easily eliminated from the body and participates in the cell redox reactions, where ROS generate through Fenton reactions, increased iron concentrations could damage proteins, lipids and DNA permanently, causing structural and functional impairments. High plasma iron concentrations may amplify the effect of free radicals (Aksu, 2010); although cells have developed different mechanisms to reduce iron toxicity, including the regulation of iron transport through cell membranes and the production of ROS-eliminating enzymes. An imbalance of these systems caused by excess iron could increase oxidative damage susceptibility that could cause an increase in the mutation rate. These could increase the risk of developing neoplastic processes, diabetes and cardiovascular and neurological disease (Evans, 2004; Liu, 2009; Toxqui, 2010).

The effect of treatment with iron on DNA oxidation has been investigated in children with IDA, observing a significant increase of DNA strand breaks and baseline oxidative DNA damage as compared with children not receiving treatment (Aksu, 2010). However, we have not found evidence in the literature about the effect of preventive doses of iron supplementation on DNA. Therefore, we propose to compare the effectiveness of weekly and daily supplementation for the prevention of anemia in infants less than six months of life and to analyze their impact on genomic stability.

Objectives

General: To compare the effectiveness of weekly and daily iron supplementation for the prevention of anemia in infants.

Specific: To compare:

- To compare the effectiveness of weekly, daily and no iron supplementation at six months of age in EBF infants.
- To compare the effectiveness of weekly and daily iron supplementation in six-month-old infants receiving MF.
- To compare the incidence of adverse effects for weekly and daily iron supplementation at six months of age.
- To compare the adherence to treatment of weekly and daily iron supplementation at six months of age.
- To compare the concentration of oxidative stress biomarkers for both types of iron supplementation.

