- To compare the genomic damage in both types of iron supplementation.

Study hypothesis

Weekly ferrous sulfate supplementation will be more effective in the prevention of IDA in infants than daily supplementation due to a higher adherence and a lower incidence of adverse effects. Weekly iron supplementation will cause less genomic instability as compared with daily iron supplementation.

Study design

Randomized controlled clinical trial.

Study sample

Eligibility

Infants performing monthly health controls at the Pediatric Health Observatory of IDIP, La Plata Children's Hospital, from birth to six months of age will be included in the study.

Inclusion, exclusion and elimination criteria

Inclusion criteria: Three-month-old clinically healthy breastfeeding infants with birth age > 37 weeks, birth weight between 2500 and 4000 g, a normal fetal and neonatal history, that attend IDIP's Health Observatory and whose parents/guardians express the will to participate in the study and sign a written informed consent form.

Exclusion criteria: Anemic and/or iron deficient infants or with chronic diseases or acute infections or under antibiotic/vitamin treatment within 15 days prior to the study.

Elimination criteria: infants with severe intolerance to iron preventive supplementation, who will receive the alternative preventive treatment with ferrous fumarate or iron polymaltose complex).

Unit of analysis: Three to six month-old infants.

Sample size and selection

According to ENNyS, the prevalence of anemia in 6-9 months old infants is 50.8%. Our controlled interventions would reduce such prevalence to 30%. Sample size was estimated with 0.95 significance level and 0.80 power, resulting in 174 infants (n= 87 for each supplementation group). This number was adjusted considering a 15% dropout, thus enrolling 204 infants.

Methods

Operational definition of variables

Main variables

-Anemia is defined as the “decrease in the total amount of blood cells or a blood hemoglobin (Hb) concentration more than 2 standard deviations below the mean of an age- and sex-matched reference range”. We will define the presence of anemia when Hb < 9.5 g/dL at 3 months of age and Hb < 11.0 g/dL at six months of age (CDC, 2007).

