- Genomic damage: DNA damage assessed by cytomolecular techniques using the Comet assay (damage index assessment in 200 cells, quantifying damage by Tail moment and Olive Tail moment). The frequency of oxidized DNA bases will be determined by competitive 8-oxo-dG Elisa.

Other variables:

- Sex, weeks of gestation, umbilical cord clamping.

- Infant nutritional condition will be assessed by anthropometry (weight, height, head circumference) at three and six months.

- Sociodemographic data of infants and relatives, including place of residence, unsatisfied basic needs, maternal education.

- Maternal nutritional condition will be evaluated with anthropometry and iron status.

- Environmental exposure to genotoxic agents (antibiotics, radiation (X-rays) and chemical substances like pesticides, solvents and industrial waste) will be assessed by questionnaire.

Data collection

-Patient enrolment

During health control visits to IDIP Health Observatory on the first and second month of life, parents and tutors will be invited to participate in the study; the study's protocol, its aims and benefits will be explained in a plain language. They will be asked to sign a written informed consent form in case they accept their children be incorporated to the study. Infants meeting the inclusion criteria with exclusively breastfeeding (EBF) will be randomly divided into three groups: weekly, daily and no supplementation. Those with mixed feeding (breastfeeding and formula; MF) will be randomly divided into two groups: weekly and daily supplementation.

- Intervention

Weekly supplementation (EBF or MF): infants will receive a weekly dose of ferrous sulfate (4mg/kg/week).

Daily supplementation (EBF or MF): infants will receive a daily dose of ferrous sulfate (1 mg/kg/day).

Without intervention (only EBF): infants will receive no supplementation, following the current SAP guidelines. Ferrous sulfate will be supplied by pediatricians.

- Randomization

Randomization will be performed by computer-generated random sequences of numbers in blocks of variable length. Randomization will be stratified by type of intake (EBF or MF).

Treatment assignments will be placed in sequentially numbered, opaque and sealed envelopes which will be consecutively put in a box and later removed one at a time. The person in charge of the random allocation process will not take part in the enrollment process.

- Blinding

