Blood samples (3 ml) from infants will be drawn at IDIP’s laboratory by venipuncture and divided into two vials: 1) an EDTA tube containing 1 ml blood for complete blood count, and 2) lyophilized lithium heparin tube that will be centrifuged to obtain plasma for the assessment of ferritin, CPR, sTfR, 8-oxodG and TBARS, and erythrocytes for the assessment of CAT and SOD determinations and for the Comet assay. The following methods will be used:

Hemoglobin: Modified Drabkin method (ABX Pentra DX 120 Horiba).

Ferritin and sTfR: enzymatic immunoassay using a chemiluminescence substrate (Access-Beckman Coulter, Fullerton, US).

C-reactive protein: turbidimetry (Autoanalyzer BT 3000 Plus Wiener).

All these tests will be performed at the Children’s Hospital Central Laboratory.

Cytomolecular genomic stability: alkaline version of the Comet assay (electrophoresis of a cell sample previously embedded in agarose, being migration proportional to the damage present (Sinh et al., 1988, Padula 2016).

ROS-mediated DNA damage: ELISA to quantify 8-oxodG, the most frequently oxidized nucleotide (Rossner et al 2006; Rossner & Sram 2012).

These tests will be performed at IGEVET.

CAT activity: spectrophotometry using Aebi’s method.

SOD activity: commercial kit (Ransod; RandoxLabs).

TBARS: spectrophotometry according to Okhawa.

These tests will be performed at IDIP and IGEVET.

Iron nutritional status (hemoglobin and ferritin) of mothers: blood samples taken at three and six months after delivery.

Data analysis

The effectiveness of the interventions will be evaluated at six months of age by comparing the incidence of anemia in both study groups as a relative risk (RR) and its corresponding 95% confidence interval (95% CI). For the EBF group, no supplementation will be the reference category, whilst for the MF group, the reference category will be daily iron supplementation.

Intention-to-treat analysis will be used to account for the possible changes in type of feeding and/or intervention arms. However, per-protocol analysis will be also performed and compared with intention-to-treat analysis in order to determine the result robustness.

Losses to follow-up will be censored since analyses will be performed in closed cohorts because we will not be able to estimate incidence density (we will only collect data on anemia and ID at three and six months).

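### The stated 80% power with 87 infants per group fits none of the trial's comparisons: the unsupplemented arm is not counted, the analysis is split by feeding type, and 50.8% versus 30% is not a weekly-versus-daily difference

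*Protocol*

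**What the plan says.** Sample size and selection takes its starting risk from a national survey: "According to ENNyS, the prevalence of anemia in 6-9 months old infants is 50.8" percent. The assumed effect is "Our controlled interventions would reduce such prevalence to 30" percent, a single figure for the interventions together. The result is "Sample size was estimated with 0.95 significance level and 0.80 power, resulting in 174 infants (n= 87 for each supplementation group"). Allowance for loss follows: "This number was adjusted considering a 15% dropout, thus enrolling 204 infants".

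The main question is stated in Objectives: "General: To compare the effectiveness of weekly and daily iron supplementation for the prevention of anemia in infants". The Study hypothesis gives it a direction: "Weekly ferrous sulfate supplementation will be more effective in the prevention of IDA in infants than daily supplementation".

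The design has five arms. Under Data collection, Patient enrolment: "Infants meeting the inclusion criteria with exclusively breastfeeding (EBF) will be randomly divided into three groups: weekly, daily and no supplementation". MF infants are randomised to weekly or daily, and randomisation is stratified by feeding type. Data analysis then sets a different reference for each stratum: "For the EBF group, no supplementation will be the reference category, whilst for the MF group, the reference category will be daily iron supplementation".

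The protocol gives no expected EBF:MF split, no number for the unsupplemented arm, and no expected difference between weekly and daily.

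**The concern.** The sample size describes a trial with two groups and one comparison. The protocol describes five arms in two strata. They disagree on three points.

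- **Who is counted.** The 174 is used up by two supplementation groups of 87. The unsupplemented EBF arm is the reference for the first specific objective, yet it has no infants in the calculation.
- **Which contrast is tested.** The analysis works within EBF and within MF, so each contrast has only part of 87 on each side.
- **Which effect is assumed.** The drop from 50.8% to 30% is what supplementation is expected to achieve against the survey level. Weekly versus daily compares two supplemented arms, and no difference is assumed for it.

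The summary says the results are expected to support revising current supplementation schedules. If weekly and daily do not differ significantly, a reader relying on the stated 80% power could take the two as equally effective when the trial had little chance of separating them.

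A smaller point is that 0.95 is called the significance level. It can only mean 95% confidence, that is, alpha 0.05.

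**Working it through.** **Inputs from the protocol.** p1 = 0.508, p2 = 0.30, power 0.80, 87 per group, 15% dropout, 204 enrolled, three EBF arms and two MF arms. Alpha is read as 0.05. Sidedness is not stated.

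**Inputs assumed.** Equal allocation within each stratum; EBF share f varied from 30% to 80%, with the extremes 0% and 100% noted.

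**Step 1: reproduce the plan's figure.** With p̄ = (p1 + p2)/2 = 0.404,

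n = [1.96·√(2p̄(1−p̄)) + 0.8416·√(p1(1−p1) + p2(1−p2))]² / (p1−p2)²

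= (1.3601 + 0.5708)² / 0.208² = 86.2, rounded up to 87 per group, 174 in total.

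A one-sided test gives 68 and a continuity correction gives 96, so the two-sided 0.05 test without correction is the one used. For dropout, 174/0.85 = 204.7 against the stated 204; the rounding is immaterial. The 204 is therefore the two groups of 87 plus loss, with nothing added for a third group.

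**Step 2: evaluable infants per arm.** 204 × 0.85 = 173.4 in total. Each EBF arm has 173.4·f/3 and each MF arm 173.4·(1−f)/2. Weekly or daily pooled over strata is the sum of the two.

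**Step 3: power for 50.8% versus 30% at those sizes.** With n per side,

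power = Φ{[0.208 − 1.96·√(2p̄(1−p̄)/n)] / √[(p1(1−p1) + p2(1−p2))/n]}

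For f = 60% (five equal arms), n = 34.7: (0.208 − 1.96 × 0.1178)/0.1152 = −0.20, so power is 42%.

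| EBF share | per EBF arm | power, EBF pair | per MF arm | power, MF pair | pooled weekly or daily | power, pooled |
|---|---|---|---|---|---|---|
| 30% | 17 | 23% | 61 | 65% | 78 | 76% |
| 50% | 29 | 36% | 43 | 51% | 72 | 73% |
| 60% | 35 | 42% | 35 | 42% | 69 | 71% |
| 80% | 46 | 53% | 17 | 23% | 64 | 67% |

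At the extreme of all infants EBF, there are 58 per arm and 63% power for one supplemented arm against none. Combining both supplemented arms against none in that case gives 76%. At the other extreme of all infants MF, there are 87 per arm and 80% power, but the EBF objective has no infants.

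**Step 4: the effect that the hypothesis needs.** Suppose the daily arm reaches the 30% that the plan expects of its interventions.

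- At 87 per group, power is 33% for a weekly risk of 20% and 66% for 15%.
- At 87 per group, the weekly risk must be about 12.7% or lower for 80% power. At 72 per group (f = 50%) it must be about 11.3%, and power for 20% falls to 28%.
- For 80% power, 30% versus 20% needs 294 per group, and 30% versus 15% needs 121.

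**Step 5: scale of the gap.** Holding 87 evaluable infants in all five arms would need 5 × 87 = 435 evaluable, and 435/0.85 = 512 enrolled, against 204.

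**The case against.** The best defence is that the arithmetic is right and the sample size was meant for weekly versus daily pooled over feeding types. The general objective and the hypothesis are worded that way, the 87 is given per supplementation group, and the first sentence of Data analysis speaks of two study groups. The unsupplemented infants might also be additional to the 204. In that case pooled weekly versus daily would keep 87 per group and 80% power for 50.8% versus 30%. Further, the EBF share and the weekly risk of 20% are not in the protocol, and relative risks with 95% confidence intervals would themselves show any imprecision.

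Part of this stands. Nothing is miscalculated, the power figures depend on a declared range of splits, and the weekly-risk figures are illustrations. The rest does not restore the stated power:

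- Directly after mentioning two groups, Data analysis sets a separate reference for each feeding type, so the pooled comparison is not the one specified.
- The protocol gives 204 as the enrolment and mentions no infants beyond it.
- Even if the unsupplemented infants were extra, the within-stratum contrasts would stay short. Half EBF would give 43.5 per supplemented arm and 51% power.
- On any reading, 50.8% versus 30% is not a difference between two supplemented arms.
- A confidence interval shows imprecision, but it does not correct a stated power.

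**Conclusion.** The concern holds. The 87 per group is right for a question that the trial does not ask. Within 204 infants at 15% loss and equal allocation in each stratum, power for 50.8% versus 30% is 42% per pairwise contrast with five equal arms. Over EBF shares of 30% to 80%, it runs from 23% to 53% in EBF and from 65% down to 23% in MF. The split does not rescue the EBF objective: even an all-EBF trial gives 63% for one supplemented arm against none. Pooled weekly versus daily has 76% to 67%, and that still uses an effect that does not belong to it. With daily at 30% (an assumption taken from the plan's joint figure), even a full 87 per group detects only a weekly risk of about 12.7% or lower with 80% power. This must be corrected, because the power stated for the main question is not delivered.

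**What to change.** Keep 204 infants and rewrite the section so that it matches the design.

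1. Name weekly versus daily, pooled over EBF and MF, as the comparison that the sample size refers to. Add that comparison to Data analysis, which at present sets only stratum-specific references.
2. State the infants expected in each of the five arms, including the unsupplemented one, with the assumed EBF:MF split.
3. State the power or detectable difference actually delivered for the pooled, EBF and MF contrasts. For weekly versus daily, start from a daily-arm risk near 30% rather than 50.8%.
4. Describe the within-stratum contrasts as estimates. The relative risks with 95% confidence intervals already planned serve for this.
5. Replace the 0.95 significance level with a two-sided level of 0.05.

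The cost is protocol text in two sections, with no extra infants and no change to treatment or visits. The stated power becomes less favourable.

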Pediatricians in charge of supplementation will know the assigned intervention only when the envelopes are open. Professionals in charge of performing laboratory tests will not know intervention assignments.

-Sample collection. Surveys

Before supplementation, 3-ml blood samples from infants will be drawn to assess anemia, ID, and genomic stability. All non-anemic/iron deficient infants will be recruited and will be supplemented

according to the group assigned during 12 weeks (three months). At the end of this period (six months of age), blood samples will be drawn again to measure the study variables. Infant and family sociodemographic data will be surveyed at the first visit (three months of age). Anthropometric measurements will be taken at three and six months. Nutritional assessment of the mothers will be performed at the beginning and at the end of the study, measuring weight and height and drawing blood samples for anemia and ID assessment.

- Intervention progress monitoring

Pediatricians will prescribe iron doses and manner of administration. Parents and/or tutors will receive one or more droppers with ferrous sulfate sufficient to complete one-month supplementation, considering that all infants will perform monthly health controls. The Telegram program “LactaPlusIDIPBOT”, designed at IDIP, will be used to send reminders for iron supplement intake. They will be also contacted weekly (Facebook messenger, Whatsapp, Telegram). To monitor adherence, we will use a daily/weekly consumption record form that will be completed by parents/tutors and delivered at each health control. To determine consumption, we will control de excess volume in droppers during each monthly control.

- Record of adverse effects

Parents and/or tutors will receive a form to register adverse effects which will be presented at each monthly control. They will register intake rejection, constipation, vomiting, diarrhea, and abdominal pain. Infants with intolerance to iron supplementation will be excluded from the study but will continue on an alternative treatment (1 mg/kg/day fumarate or iron polymaltose complex).

- Laboratory tests

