We will also determine the incidence of adverse effects and the incidence of low treatment adherence at six months of age for weekly vs. daily iron supplementation in both EBF and MF and calculate RR (95% CI) at six months of age.

[figure not shown]
Means and differences of enzymatic SOD and CAT activity and TBARS concentration at three and six months will be compared in both study groups. The same will apply to the Comet and 8 oxodG assays. Differences between groups will be determined by Anova or Kruskal-Wallis test for quantitative variables with post-hoc comparisons and Chi-square for categorical variables. Within group comparisons will be analyzed using Student's or Wilcoxon test.

Risk of bias assessment

Selection bias could be present since parents/tutors willing to participate could show higher interest in the research project than those who do not participate. Considering that the population sample attends for monthly controls, a trust relationship may be established between parent/tutor and pediatrician, resulting in a higher degree of adherence to supplementation than in the general population.

Project Schedule

Study flowchart

Work plan

SPECIFIC OBJECTIVE 1: Compare the effectiveness of weekly, daily and no iron supplementation in EBF infants.

SPECIFIC OBJECTIVE 2: Compare the effectiveness of weekly, daily and no iron supplementation in MF infants.

| ACTIVITY | RESPONSIBLE | EXPECTED RESULT |
|--|----------------------------|--|
| Enrollment of infants according to the inclusion criteria. | Pediatricians | Incorporate infants who comply with inclusion criteria |
| Informed consent. | | |
| Intervention assignment. | Statistician | Random allocation |
| Blood sample collection. | Laboratory technician | Adequate specimen collection (enough volume, non clotted) |
| Hemoglobin, ferritin, PCR and sTfR determinations. | Biochemists | Assessment of the prevalence of anemia and iron deficiency |
| Indication for and monitoring of the intervention | Pediatricians | Complete registry of the intervention. |
| Text message reminders | Pediatricians | Intervention adherence. |
| Weight and height measurement. | Pediatrician, Nutritionist | Determine the anthropometric nutritional condition. |
| Registry of data. | Data entry | Complete database. |
| Data analysis and interpretation of results. | Team, Statistician | Report of results and conclusions. |

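### The main anemia relative risk names no adjustment for 3-month hemoglobin, although it is measured in every infant: precision is lost, but the comparison is not biased

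*Protocol*

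**What the plan says.** Under Operational definition of variables, anemia is "Hb < 9.5 g/dL at 3 months of age and Hb < 11.0 g/dL at six months of age". The eligibility section reads: "Exclusion criteria: Anemic and/or iron deficient infants or with chronic diseases or acute infections". Read with the 3-month cut-off, this admits an iron-replete infant whose Hb lies between 9.5 and 10.9 g/dL.

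Under Sample collection, "Before supplementation, 3-ml blood samples from infants will be drawn to assess anemia, ID, and genomic stability", so the starting value exists for every enrolled infant. The Randomization paragraph says "Randomization will be stratified by type of intake (EBF or MF"); Hb is not a stratification factor.

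The Data analysis section evaluates effectiveness at six months by "comparing the incidence of anemia in both study groups as a relative risk (RR) and its corresponding 95% confidence interval (95% CI"). It gives each feeding group its own reference arm and plans intention-to-treat and per-protocol analyses. It names no covariate. For the oxidative-stress markers the same section does use the 3-month value: "Means and differences of enzymatic SOD and CAT activity and TBARS concentration at three and six months will be compared in both study groups".

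**The concern.** An infant who enters at 10.5 g/dL and stays there counts as a case at six months. An infant who enters at 12.5 g/dL must fall by more than 12.5 − 11.0 = 1.5 g/dL to count. If 3-month and 6-month Hb are at all positively correlated, starting Hb predicts the outcome, and nothing in the design balances it between arms.

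The effectiveness comparisons are made separately in exclusively breastfed (EBF) and mixed-fed (MF) infants, over five arms in all. Arms inside a stratum may therefore be small, and a chance difference in starting Hb can move the estimated RR noticeably. A measured baseline value that predicts the outcome can reduce this noise at almost no cost.

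**Working it through.** **1. The plan's own figure.** The inputs are in Sample size and selection: "the prevalence of anemia in 6-9 months old infants is 50.8" per cent, and "Our controlled interventions would reduce such prevalence to 30" per cent, with 0.80 power. Its significance level of 0.95 is read as two-sided alpha 0.05. With mean proportion (0.508 + 0.30)/2 = 0.404 and difference 0.208:

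n = [1.960·√(2·0.404·0.596) + 0.842·√(0.508·0.492 + 0.30·0.70)]² / 0.208² = (1.360 + 0.571)² / 0.0433 ≈ 86.2, so 87 per group and 174 in total.

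This matches the plan. For dropout, 174/0.85 = 204.7, against the stated 204. The size rests on an unadjusted comparison of two proportions.

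**2. Share entering below 11.0 g/dL.** The documents give no Hb distribution. Assume 3-month Hb is normal with SD 0.9 and truncated at 9.5. The share is [Φ((11.0−m)/0.9) − Φ((9.5−m)/0.9)] / [1 − Φ((9.5−m)/0.9)].

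- m = 10.8: (0.588 − 0.074)/0.926 ≈ 56%
- m = 10.5: about 67%
- m = 11.5: about 28%

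The iron-deficiency exclusion is not modelled and could change these shares.

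**3. Chance imbalance.** If half the infants enter below 11.0, the between-arm difference in that share has SD √(2·0.5·0.5/n).

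- n = 87: 7.6 points, 95% within about 15 points
- n = 40 (assumed, as inside a stratum): 11.2 points, 95% within about 22 points
- n = 174/5 = 34.8 (five equal arms, assumed): 12.0 points, 95% within about 23 points

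At an assumed 3-to-6-month correlation of 0.5 and m = 10.8, control risk at six months is about 66% for infants entering below 11.0 and 32% for the rest. A 15-point imbalance then shifts the unadjusted risk difference by 0.15 × (0.661 − 0.317) ≈ 5 points, against a planned 20.8.

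**4. Gain from adjustment, 87 per arm.** Simulations used 3-month Hb as in step 2 (mean 10.8 or 10.9), a correlated 6-month Hb and the outcome Hb < 11.0 g/dL. Event rates were at or near the planned ones (30/50.8 = 0.59; true RR about 0.57 in one set-up). The last column is an arithmetic check. It starts at 80% power and divides 1.960 + 0.842 = 2.802 by the square root of the variance ratio; power is then Φ(that value − 1.960).

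| Correlation | Fall in variance of log RR | Simulated power gain | Power from the variance fall alone |
|---|---|---|---|
| 0 | about 0% | none | 80% |
| 0.3 | 3–6% | 1–3 points | 81–82% |
| 0.5 | 10–13% | 4–7 points | 84–85% |
| 0.7 | 21–26% | 8–12 points | 88–90% |

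The arithmetic supports the lower to middle part of each simulated range. The average RR did not move.

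A check on the risk-difference scale, with a baseline-adjusted linear model and robust standard errors, gave variance ratios of 1.01, 0.96, 0.85 and 0.70. Unadjusted to adjusted power was 80 to 80, 82 to 83, 82 to 86 and 81 to 91%. At correlation 0.5, type I error was 5.8% unadjusted and 5.0% adjusted (nominal 5%).

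**5. Smaller arms.** On the same risk-difference scale with an assumed 40 per arm, power goes from 50 to 49% at correlation 0, 48 to 49% at 0.3, 51 to 55% at 0.5 and 48 to 62% at 0.7.

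**The case against.** The strongest reply is that nothing here is wrong. Under randomization the unadjusted RR is valid, and its confidence interval already allows for chance imbalance in starting Hb. The same can be said of any prognostic variable in any trial. This stands: the point is about efficiency.

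A second reply is that covariates are usually listed in a statistical analysis plan, which is not shown. The protocol never calls its RR unadjusted, and an adjusted RR would fit its wording. This also stands as a limit, and the finding goes no further than that no covariate is named. The protocol does, however, already fix the effect measure, interval, reference arms and analysis sets. Naming the covariate there would close off a later choice between adjusted and unadjusted results.

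Third, the size depends wholly on assumed Hb values and, for small arms, on assumed stratum sizes. That is correct. At correlations of 0 to 0.3 the gain is negligible or small.

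Two stronger readings are tempting. A reader might infer that two different cut-offs bias the comparison or misclassify infants as new cases. The documents do not support this: anemia is defined against an age-matched reference, both cut-offs apply equally to all arms, and an infant at 10.5 g/dL is non-anemic at three months and anemic at six by that definition. The term incidence is therefore correct. A reader might also infer that starting Hb is known to be a strong determinant of the outcome here; the documents give no correlation to show it.

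**Conclusion.** The point holds as a minor improvement. The protocol collects 3-month Hb in every infant, admits infants across a range that straddles the six-month cut-off, does not stratify on Hb, and names no adjustment in the main anemia comparison. The consequence is avoidable variance and exposure to chance imbalance, without bias.

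The benefit is worth having if the 3-to-6-month correlation is about 0.5 or more: roughly 4 to 12 power points at 87 per arm, with log RR variance lower by 10 to 26%. It is small at 0.3 and absent at 0, where the cost of adjusting is also close to nil. The direction holds for any positive correlation. The size rests on the assumed Hb mean, SD and correlation, and on ignoring the iron-deficiency exclusion when modelling entry Hb.

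**What to change.** In Data analysis, prespecify that the primary anemia RR comes from a modified Poisson model (log link, robust variance) with arm and continuous 3-month Hb, fitted within each feeding stratum and with the reference arms already chosen. Report the unadjusted RR with its 95% CI as a sensitivity analysis. Keep both age-specific cut-offs and the term incidence of anemia.

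The cost is a sentence or two of analysis text. No new measurement, visit, sample-size change or change in care is needed.
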